3.0 Inclusion and Exclusion Criteria

3.1 Inclusion Criteria

1. Pregnant Female Patients greater than or equal to 18 years of age
2. Induction of labor for a single live intrauterine pregnancy
 - a. For medical indications for induction of labor, must be greater than or equal to 37 weeks gestational age and meet one of the following criteria for the induction of labor (taken from ACOG Practice Bulletin Number 107) [2]
 - i. Abruptio placentae
 - ii. Chorioamnionitis
 - iii. Gestational hypertension
 - iv. Late term (≥ 41 weeks) or postterm (≥ 42 weeks) pregnancy
 - v. Maternal medical conditions (eg, diabetes mellitus, renal disease, chronic pulmonary disease, chronic hypertension, antiphospholipid syndrome)
 - vi. Fetal compromise (eg, isoimmunization, oligohydramnios)

- b. For elective inductions of labor that do not meet the above medical indications, must be greater than or equal to 39 weeks gestational age and meet one of the following criteria.
 - i. Ultrasound measurement at less than 20 weeks of gestation supporting gestational age of 39 weeks or greater
 - ii. Fetal heart tones documented as present for 30 weeks by Doppler ultrasonography
 - iii. 36 weeks since positive serum or urine human chorionic gonadotropin pregnancy test result
 - iv. Documented fetal lung maturity
3. Cephalic presentation
4. 20 minute reassuring fetal heart rate (reactive nonstress test (NST))
5. Bishop score based on sterile vaginal exam of less than or equal to 6, for which the cervical dilation is less than or equal to 2 cm.
6. Equal to 3 or less uterine contractions over 10 minutes

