8.0 Subject Numbers and Statistical Plan

8.1 Number of Subjects

A total of 110 subjects will be randomized.

From looking at previous data collected at Penn State Hershey Medical Center, there were about 350 induction of labors using misoprostol over one year's time. Due to inclusion/exclusion criteria it is estimated that only 60% of the induction of labors will qualify for the study. That leaves about 210 patients able to participate in the study. Potentially the study could be completed within six months.

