10.8 Suspension of research

If the total number of subjects experiencing one or more TESAE (defined as uterine rupture, maternal death during her hospitalization, neonatal death (0-28 days of life) related to the study drug, and cesarean hysterectomy) reaches 5, the trial will be stopped. This reflects a 2.3% prevalence rate (110 subjects with 110 singleton neonates are included in the trial for a prevalence of 5/220 subjects). Or if any two cases of uterine rupture, two cases of maternal death during her hospitalization, or two cases of neonatal death (0-28 days of life) related to the study drug, the trial will be stopped.

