19.6 Stopping Rules

If the total number of subjects experiencing one or more serious adverse events (defined as uterine rupture, maternal death during her hospitalization, neonatal death during maternal hospitalization, and cesarean hysterectomy) reaches 5, the trial will be stopped. This reflects a 2.3% prevalence rate (110 subjects with 110 singleton neonates are included in the trial for a prevalence of 5/220 subjects). Or if any two cases of uterine rupture, two cases of maternal death during her hospitalization, or two cases of neonatal death (0-28 days of life) related to the study drug, the trial will be stopped.

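### The five-subject stopping limit is presented as a 2.3% rate (5/220), but per randomized woman it is reached at 5/110 = 4.5%, and sections 10.8 and 19.6 define its neonatal component differently

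*Combined protocol and SAP*

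**What the plan says.** Section 10.8 has two stopping clauses. The first is a composite count, and it opens with "If the total number of subjects experiencing one or more TESAE". Four events qualify: rupture of the uterus, death of the mother in hospital, hysterectomy at cesarean, and a drug-related death of the neonate within 28 days. The trial stops at a count of five. That count is explained by a rate: "This reflects a 2.3% prevalence rate (110 subjects with 110 singleton neonates are included in the trial for a prevalence of 5/220 subjects". The second clause acts on single event types: "Or if any two cases of uterine rupture, two cases of maternal death during her hospitalization, or two cases of neonatal death", the neonatal deaths being those within 28 days that are related to the study drug. Cesarean hysterectomy has no two-case clause.

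Section 19.6 repeats the count of five, the 2.3% and the two-case clause. Its composite, however, names a different neonatal event: "maternal death during her hospitalization, neonatal death during maternal hospitalization, and cesarean hysterectomy) reaches 5, the trial will be stopped". Drug-relatedness is not required there, and the time window is the mother's stay rather than 28 days.

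Section 8.1 fixes the unit used elsewhere in the plan: "A total of 110 subjects will be randomized". Section 3.1 restricts entry to singleton pregnancies ("Induction of labor for a single live intrauterine pregnancy"), so 110 women means 110 neonates.

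**The concern.** The explanatory sentence uses the word subjects in two senses. It first sets 110 neonates beside 110 subjects, then divides by 220 subjects. Rupture, maternal death and hysterectomy can happen only to the women, and neonatal death only to the neonates, so no listed event has 220 people at risk. Read with the plan's usual meaning of a subject, the 2.3% is half the rate at which the limit is reached.

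These two clauses are the only numerical stopping triggers in the plan, because section 10.7 says that the six-monthly Fisher tests do not decide stopping. A reader who takes 2.3% as the per-woman rate guarded by the composite clause would be misled by a factor of two. The differing neonatal definitions raise a further problem: they can change whether the trial stops at all.

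**Working it through.** **Inputs.** Limit of 5 subjects (10.8, 19.6); 110 randomized women (8.1); singleton pregnancies, so 110 neonates (3.1); two-case clause for rupture, maternal death and drug-related neonatal death (10.8, 19.6).

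**1. The plan's figure.** 5/(110 + 110) = 5/220 = 2.27%, which rounds to the stated 2.3%. The division is correct.

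**2. Rate per randomized woman or mother-infant pair.** 5/110 = 4.55%. The ratio to the stated rate is 220/110 = 2.

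**3. Reaching the limit and staying below it.** The clause acts when the count reaches five, so four affected women do not trigger it. The interim points of 55 and 30 women are chosen for illustration.

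| Women enrolled | Limit reached (5/n) | Highest rate not triggering it (4/n) |
|---|---|---|
| 110 | 4.5% | 3.6% |
| 55 | 9.1% | 7.3% |
| 30 | 16.7% | 13.3% |

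**4. Two-case clause.** 2/110 = 1.8% at full enrolment and 2/55 = 3.6% at half, for each of the three events it covers.

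**5. How the clauses interact under 10.8.** Before the two-case clause acts there can be at most one rupture, one maternal death and one drug-related neonatal death. These involve at most three subjects. Reaching five without that clause having acted therefore needs at least 5 - 3 = 2 subjects whose only event was a hysterectomy.

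**6. The same check under 19.6.** The composite there counts any neonatal death during the mother's stay, while the two-case clause counts only drug-related deaths. Five such deaths judged unrelated would reach five with no hysterectomy and no two-case trigger, so step 5 does not carry over. Under 10.8 those five deaths would count as zero. In the other direction, a drug-related neonatal death within 28 days but after the mother's discharge counts in the 10.8 composite and not in that of 19.6.

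**7. What the unit does to the operating characteristics.** Assume independent women, full enrolment and the five-subject clause alone. With X ~ Binomial(110, p):
- p = 2.27% per woman: P(X ≥ 5) = 11%
- p = 4.55% per woman: P(X ≥ 5) = 56%
- a 50% chance of reaching five needs p of about 4.2%, and an 80% chance about 6.0%

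For comparison, 220 persons each at 2.27% also give 56%. So 2.3% per person and 4.5% per pair describe nearly the same limit in different units, whereas 2.3% per woman does not. For a single event type covered by the two-case clause, p = 2.27% gives P(X ≥ 2) = 72%.

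**The case against.** The strongest reply is that nothing has been miscalculated. The sentence prints the count, both 110s and the 220. The composite mixes maternal and neonatal events, so five per 220 persons is a coherent per-person rate. The trial acts on the count, and correcting the percentage alters no trigger, analysis or sample size. All of that stands. The fault is an undefined unit, not the division. If mothers and neonates were counted separately, an affected mother and her affected neonate would count as two, and five persons could come from four pairs (4/110 = 3.6%). The plan does not say that it counts this way, and section 8.1 points to women.

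It is also fair to say that a rising rate at smaller n is a property of any fixed count, and that the plan ties its figure to all 110 women. The early-enrolment rates illustrate this and are not a separate error.

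Three stronger readings are tempting, and the documents do not support them:
- **That the rule tolerates at least 4.5% of women.** It stops at that rate; the most it lets pass at full enrolment is 3.6%.
- **That the trial allows twice the stated rate of every catastrophic event.** For rupture, maternal death and drug-related neonatal death the two-case clause acts at 1.8%, below 2.3%.
- **That the five-subject clause works only through hysterectomy.** Under 10.8 at least two hysterectomy-only subjects are needed, but other events can supply the remaining three. Under 19.6 none is needed.

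Nor do the documents say that the IRB judged acceptability from the 2.3%. Section 10.2 has these events reported to the IRB within 24 hours.

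**Conclusion.** The 2.3% is wrong as a rate per subject in the plan's own sense of the word. Per randomized woman or pair, the composite limit is reached at 4.5% at full enrolment, a factor of two, and at a higher rate if reached sooner. This rests on subject meaning a randomized woman, as in section 8.1. If each person is counted separately, 5/220 holds at full enrolment, but the plan would have to say so.

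The practical reach is limited by the two-case clause, which is tighter for three of the four events listed in 10.8. The conflict between 10.8 and 19.6 over neonatal death has more operational weight than the percentage, because the same events could stop the trial under one section and not the other. The correction is worthwhile and cheap. It does not show that the limit of five is too high or too low.

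**What to change.** In sections 10.8 and 19.6:

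- State what is counted: the randomized woman (mother-infant pair), or each mother and each neonate separately.
- Replace the 2.3% and the 220 denominator with the rate on that unit. For a count of five per woman or pair this is 5/110 = 4.5% at full enrolment, with a note that the rate is higher if the limit is reached earlier.
- The investigators and the IRB should reconcile the count of five with the stated 2.3%, since per woman the two do not describe the same limit.
- They should also reconcile the neonatal-death definition in the 10.8 composite with that in the 19.6 composite, and each with the two-case clause.

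This review proposes no threshold and does not say which definition should stand. The cost is a few sentences in a protocol amendment and, on the per-woman unit, a less favourable stated figure.

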1.3 Secondary Study Endpoints

1. Time interval from administration of misoprostol to initiation of oxytocin for continued augmentation of labor
2. Time interval from administration of misoprostol to vaginal delivery
3. Cesarean section rate
4. Rate of vaginal delivery within 24 hours
5. Rate of abandoning misoprostol for cervical ripening and switching to mechanical dilation for cervical ripening (ie, Foley balloon)
6. Rate of development of preeclampsia requiring magnesium sulfate administration
7. Rate of tachysystole
8. Rate of tachysystole causing non-reassuring fetal heart tones
9. Rate of need for tocolysis
10. Rate of chorioamnionitis
11. Rate of meconium stained fluid
12. Neonatal morbidity (composite outcome)
 - a. Apgar of less than 7 at 5 minutes
 - b. Fetal arterial umbilical cord gas with pH of less than 7 or base deficit great than 12
 - c. NICU admission within 4 hours of delivery
13. Maternal side effects
 - a. Rate of anti-emetic use
 - b. Rate of diarrhea
14. Treatment emergent serious adverse events
 - a. Uterine rupture
 - b. Cesarean hysterectomy
 - c. Maternal death during her hospitalization
 - d. Neonatal death (0-28 days of life) related to the study drug
15. Adverse events
 - a. Postpartum hemorrhage requiring blood transfusion
 - b. Maternal surgical ICU admission
 - c. Neonatal NICU admission during mother's hospital admission

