10.2 Data that are reviewed

Data collection for safety monitoring: Treatment emergent serious adverse events (TESAEs) are defined as uterine rupture, maternal death during her hospitalization, neonatal death (0-28 days of life) related to the study drug, and cesarean hysterectomy, and will be reported to the IRB within 24 hours of occurrence. Other adverse events that will be reviewed include postpartum hemorrhage requiring blood transfusion, surgical ICU admission, and neonatal NICU admission during mother's hospital admission.

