11.0 Risks

Subjects may experience nausea and diarrhea, which is a side effect of misoprostol; subjects may have a higher incidence of meconium stained fluid while using misoprostol; uterine tachysystole with or without nonreassuring fetal heart tones; development of chorioamnionitis; need for cesarean section; neonatal morbidity or death. All of these risks are standard risks of labor and delivery should not be any higher incidence due to the study. There is always a discomfort with sterile vaginal exams. As part of the randomization, if the subject is selected to be in the misoprostol administered per vagina, the placement of the medication may cause more discomfort than the subjects that take the medication by mouth.

Side Effects/Risks of Misoprostol:

- Diarrhea: when taking misoprostol 800 mcg daily, trials have shown an incidence of diarrhea of about 13%. In this study you will be not receive more than 300 mcg of misoprostol. [1]
- Use of vaginal misoprostol has a higher rate of uterine contractions, with contractions being more frequent than every 2 minutes when compared with placebo (RR 3.52), dinoprostone gel (RR 1.99), or oxytocin (RR 2.24) for induction of labor. [6] Induction with Foley catheter has a decreased risk of uterine contractions happening greater than every 2 minutes when compared to vaginal misoprostol (RR 0.15). [7]
- Increased risk of meconium staining of amniotic fluid, but no difference in neonatal outcome. [3,6]
- Uterine rupture [1]

Side effects of misoprostol when taken as prescribed for prevention of gastric ulcers that have an incidence greater than 1%, but no difference than placebo. [1]

- Nausea – 3.2%
- Flatulence – 2.9%
- Headache – 2.4%
- Dyspepsia – 2%
- Vomiting – 1.3%
- Constipation – 1.1%

There is a risk, as with any medication, of an unexpected allergic reaction to the study drug (defined as the development of hives, rash, swelling, or difficulty breathing) which will be treated with antihistamines in a standard fashion and lead to immediate withdrawal of the subject from the trial.

There is a risk of loss of confidentiality if protected health information or identity is obtained by someone other than the investigators, but precautions will be taken to prevent this from happening.

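### Fetal death after the first dose is in none of the TESAE lists and in neither numerical stopping rule, which count only neonatal death

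*Combined protocol and SAP*

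**What the plan says.** Section 10.2 defines the TESAEs as "uterine rupture, maternal death during her hospitalization, neonatal death (0-28 days of life) related to the study drug, and cesarean hysterectomy" and requires a report to the IRB within 24 hours. The same four events recur in 10.3, 10.8 and 20.1.2, and in 1.3 item 14, where the perinatal component is "Neonatal death (0-28 days of life) related to the study drug".

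Section 10.8 sets two numerical rules. The first stops the trial when the number of subjects with at least one listed event reaches five. The second stops it at two uterine ruptures, two maternal deaths, or "two cases of neonatal death (0-28 days of life) related to the study drug, the trial will be stopped".

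Section 19.6 restates both rules. Its five-subject list reads "uterine rupture, maternal death during her hospitalization, neonatal death during maternal hospitalization, and cesarean hysterectomy", so the neonatal item there has neither the 28-day window nor the relatedness condition. Its two-case clause matches 10.8.

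Three other places matter:

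- Section 3.1 requires "Induction of labor for a single live intrauterine pregnancy".
- Section 11.0 lists among the risks "uterine tachysystole with or without nonreassuring fetal heart tones", and also uterine rupture.
- Section 19.1 has a general, outcome-based definition of a serious adverse event that includes death.

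**The concern.** Every fetus is alive at entry, and two of the risks that section 11.0 names, tachysystole with nonreassuring heart tones and uterine rupture, can act on the fetus before it is born. The formal safety triggers start counting its death only after a live birth. Followed as written, two drug-related deaths minutes after delivery stop the trial, while two drug-related deaths minutes before delivery, with no listed maternal event, do not. The documents give no reason for the difference. The omission affects the mandatory stopping counts, the 24-hour report and the tally of serious events under secondary endpoint 14.

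**Working it through.** **1. The plan's own figure.** Sections 10.8 and 19.6 say that five events reflect 2.3%. With 110 women and 110 singleton neonates, 5 / (110 + 110) = 5/220 = 2.27%, which rounds to 2.3%. The figure reproduces. Its denominator takes all 110 fetuses to be born alive.

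**2. Whether neonatal death can be read to include fetal death.**

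| Place | Perinatal item | Live birth needed? |
|---|---|---|
| 1.3 item 14, 10.2, 10.3, 10.8, 20.1.2 | neonatal, 0 to 28 days of life, drug-related | yes |
| 19.6, five-subject count | neonatal, during the maternal stay | yes |
| 19.6, two-case clause | neonatal, 0 to 28 days of life, drug-related | yes |

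The ordinary meaning of neonatal settles each row. Section 3.3.1 agrees: it puts neonatal death among the serious events occurring after delivery, and for the period on study drug it names only uterine rupture.

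**3. What one fetal death adds to the counts.**

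- Without rupture, maternal death or cesarean hysterectomy: 0 toward five and 0 toward two, under 10.8 and under 19.6.
- With one of those events: the woman counts once toward five through the maternal event. A rupture or a maternal death also counts toward its own two-case limit.

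**4. Other routes by which it could surface.**

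- 19.1 and 19.3: the investigator can class it as serious. Nothing links that classification to the counts.
- 19.2 and 19.4: it goes to the IRB if the investigator judges it both unexpected and probably related.
- 20.1.2: unanticipated problems, as well as TESAEs, go to the IRB and FDA.
- 10.5 to 10.7: cumulative adverse events are reviewed and compared between arms every six months. Section 8.1 says that the study might be completed within six months, so the first review could fall at or after the end of enrolment.
- 1.3 item 12: a stillborn infant might register in the neonatal composite through Apgar score or cord gas. It would then be mixed with non-fatal outcomes and would trigger nothing.

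**5. How often a two-case trigger would be met once fetal death is counted.** The documents give no fetal-death rate, so p below is an assumption: the probability per pregnancy of a fetal death that meets the rule. With 110 independent pregnancies,

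P(at least 2) = 1 − (1 − p)^110 − 110 p (1 − p)^109.

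- p = 0.1%: 1 − 0.8958 − 0.0986 = 0.0056, about 0.6%.
- p = 0.5%: 1 − 0.5762 − 0.3185 = 0.1054 before rounding of the terms, about 10.5%.
- p = 1%: about 30.1%.

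Reaching five from fetal deaths alone has probability of about 0.02% at p = 0.5%, so the two-case clause is where the change has practical effect. These figures cover fetal deaths only. Pooling with neonatal deaths raises them by an amount that cannot be calculated from the documents.

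**The case against.** The strongest reply is that the plan is not blind to fetal death. The definition in 19.1 makes an adverse event that results in death serious, with no live-birth condition. Under 19.1 an event is unexpected if the clinical protocol does not list it. Section 11.0 lists neonatal death and not fetal death, so that half of the 19.4 test is probably met. Section 19.3 treats an event of unknown and questionable relationship as drug-associated for reporting, and 19.4 covers harm to individuals other than the subject. Section 10.5 requires the investigators to report risk-benefit issues to the IRB immediately, and nothing says that the numerical counts are the only grounds for stopping.

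All of this stands, and it rules out several stronger readings that a reader might infer:

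- That fetal death falls outside every serious-event definition. Section 19.1 can include it.
- That only a death at 0 to 28 days of life ever counts. The five-subject list in 19.6 has no such window.
- That fetal deaths add nothing whatever their number. Those accompanied by a listed maternal event count through that event.
- That the trial could not be stopped after stillbirths. The investigators and the IRB could act outside the counts.

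The objection does not close the gap. The other routes depend on a judgement of causality or on a periodic review, and none of them adds a case to a mandatory trigger. The neonatal item also carries a relatedness condition in most places, but once that condition is met the count moves. A fetal death equally judged to be related moves nothing.

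**Conclusion.** The point holds in this form: fetal death after the first dose is absent from all five TESAE lists and from both numerical stopping rules. An isolated fetal death contributes zero to each count and does not start the TESAE-based 24-hour report. The conclusion rests on the wording of the sections and on the ordinary meaning of neonatal; it needs no assumed rate.

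The practical size depends on a rate that the documents do not give. At assumed rates of 0.1% and 0.5%, two or more fetal deaths among 110 pregnancies would occur with probability of about 0.6% and 10.5%. A reader might infer that one or two such deaths would decide the trial's safety conclusion; the documents do not show that. The primary endpoint, its analysis and the sample size are not affected.

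**What to change.** In 1.3 item 14, 10.2, 10.3, 10.8, 19.6 and 20.1.2, add *fetal death after the first dose of study drug* alongside the existing neonatal-death item, under the same relatedness condition as that item. Count fetal and neonatal deaths together in the two-case clause and in the five-subject count.

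Add to the neonatal item and do not replace it. Replacement wording that dropped its window or its relatedness condition would make a stricter rule for neonatal deaths, which this point does not call for. Sections 10.8 and 19.6 already differ on both features in the five-subject count. They must be reconciled, but as a separate change.

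The cost is protocol wording in six places. The event is known at delivery, so no new data collection is needed. The downside is a slightly higher chance of early stopping.
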